2.3 Benefit/Risk Assessment

2.3.1 Known Potential Risks and Benefits

RPT193 is under development and has not been marketed in any country. Clinical experience is limited to safety data from the Phase 1 study, RPT193-01. To date, review of laboratory, ECG, and clinical safety assessments has not identified any significant concerns.

Based on the Phase 1 clinical data in subjects with moderate-to-severe AD, subjects treated with RPT193 as monotherapy showed signs of improvement for both signs and symptoms of AD after 4 weeks of therapy compared to placebo-treated subjects. RPT193-treated subjects demonstrated continued improvement for 2 weeks after therapy suggesting unique kinetics of clinical improvement after CCR4 inhibition, which is an upstream mechanism to decrease the inflammatory response associated with AD. Subjects enrolled in this Phase 2 study may see benefit after treatment, particularly given the 16-week length of treatment in this study.

Participation in this study will help generate future benefit for larger groups of subjects with AD and possibly other inflammatory skin diseases if RPT193 proves to be safe, well tolerated, and successful in treating this condition.

2.3.2 Assessment of Risks and Benefits

The Phase 1 clinical and safety data in healthy volunteers and subjects with moderate-to-severe AD, the favorable safety and tolerability profile, convenience of an oral medication, PK, and preliminary efficacy results support further evaluation of RPT193 in studies with larger sample sizes and longer treatment periods for the development of RPT193 as a therapy for subjects with moderate-to-severe AD and other inflammatory diseases.

All quality, pharmacology and toxicology data, and satisfactory safety results demonstrated in non-clinical studies are considered sufficient to expect a positive benefit/risk ratio for the treatment of subjects with moderate-to-severe AD and thus initiate the study.

The risk to subjects in this trial will be minimized by compliance with the eligibility criteria, proper study design, and close monitoring.

More detailed information about the known and expected benefits and risks and reasonably expected AEs of RPT193 may be found in the Investigator's Brochure.

3.0 OBJECTIVES AND ENDPOINTS

Table 1 Study Objectives and Endpoints

Objectives	Endpoints
Primary	

 To evaluate the clinical efficacy of RPT193 administered orally QD for 16 weeks to subjects with moderate-to-severe AD. 	
 % change in EASI from baseline at Week 16.

 To evaluate the safety and tolerability of RPT193 administered orally QD for 16 weeks. 	
 Incidence of treatment-emergent adverse events.
Key Secondary	

 To evaluate the efficacy of RPT193 administered orally QD for 16 weeks to subjects with moderate-to-severe AD. 	
 % of subjects achieving a Validated Investigator Global Assessment (vIGA) score of 0 or 1 at Week 16. % of subjects achieving EASI-75, defined as a 75% reduction in EASI from baseline to Week 16.

 To evaluate the efficacy of RPT193 administered orally QD for 16 weeks to subjects with moderate-to-severe AD on subject reported symptoms associated with AD. Itch peak pruritus numerical rating scale (PP-NRS) [Yosipovitch 2019]). 	
 % change from baseline in PP-NRS from an itch daily e-Diary at Week 16.
Secondary	

 To evaluate the efficacy of RPT193 administered orally QD for 16 weeks to subjects with moderate-to-severe AD. To evaluate the efficacy of RPT193 administered orally QD for 16 weeks to subjects with moderate-to-severe AD on subject reported symptoms associated with AD. Itch PP-NRS (Yosipovitch, 2019). 	
 % of subjects achieving EASI 50, defined as a 50% reduction in EASI from baseline to Week 16. % of subjects achieving EASI 90, defined as a 90% reduction in EASI from baseline to Week 16. % of subjects achieving at least 2-point reduction in vIGA score from baseline to Week 16. % of subjects achieving EASI-75 from baseline to Week 2, 4, 8, and 12. % of subjects achieving EASI-50 from baseline to Week 2, 4, 8, and 12. % of subjects achieving EASI-90 from baseline to Week 2, 4, 8, and 12. % of subjects achieving at least 2-point reduction in vIGA score from baseline to Week 2, 4, 8, and 12. Time to achieving EASI-75 from baseline. Time to achieving EASI-50 from baseline. Time to achieving EASI-90 from baseline. Change from baseline PP-NRS from an itch daily electronic Diary (e-Diary) at Week 16. For subjects with baseline PP-NRS ≥ 4:

Objectives	Endpoints
	
 ○ % of subjects achieving ≥ 4-point reduction in PP-NRS from baseline at Week 2, 4, 8, 12, and 16. ○ Time to achieving ≥ 4-point reduction in PP-NRS from baseline. ● For subjects with baseline PP-NRS ≥ 3: 
 ○ % of subjects achieving ≥ 3-point reduction in PP-NRS from baseline at Week 2, 4, 8, 12, and 16. ○ Time to achieving ≥ 3-point reduction in PP-NRS from baseline.
Exploratory (Clinical)	

 ● To evaluate the clinical efficacy of RPT193 administered orally QD for 16 weeks to subjects with moderate-to-severe AD. 	
 ● % change in SCORAD from baseline at Week 2, 4, 8, 12, and 16. ● % change in BSA from baseline at Week 2, 4, 8, 12, and 16.

 ● To evaluate the efficacy of RPT193 administered orally QD for 16 weeks to subjects with moderate-to-severe AD on subject reported symptoms associated with AD. 	
 ● Change from baseline to Week 16 in: 
 ○ Sleep quality (visual analog scale [VAS] from SCORAD) ○ Patient-oriented eczema measure (POEM) ○ DLQI ○ Skin pain NRS ○ Patient global assessment (PtGA) ○ Atopic dermatitis sleep scale (ADSS) ○  ○ Asthma Control Questionnaire (ACQ-5) (in subjects with a history of asthma) ● % of subjects achieving a PtGA score of 0 or 1 and a ≥ 2 point reduction from baseline at Week 2, 4, 8, 12, and 16.

 ● To evaluate the efficacy of RPT193 administered orally QD for 16 weeks to subjects with moderate-to-severe AD in subject subpopulations. 	
 ● % change in EASI in the following subgroups: 
 ○ Prior treatment with dupilumab or tralokinumab (Yes or No) ○ Baseline EASI score of < 21 or ≥ 21 ○ Baseline %BSA of AD affected skin $< 50\%$ or $\geq 50\%$ ○ Baseline vIGA score (3 or 4) ○ Age group ○ Race ○ Ethnicity ○ Pretreatment CCL17 levels ○ Pretreatment CCL22 levels.

Objectives	Endpoints

 Explore durability of treatment effect in those who have demonstrated an objective response at Week 16. 	
 Proportion of subjects maintaining EASI-50 at Weeks 18, 20, 24 among those achieving an EASI-50 at Week 16 and not receiving rescue therapy from Week 8 to Week 16. Proportion of subjects maintaining EASI-75 at Weeks 18, 20, 24 among those achieving an EASI-75 at Week 16 and not receiving rescue therapy from Week 8 to Week 16. Proportion of subjects maintaining EASI-90 at Weeks 18, 20, 24 among those achieving an EASI-90 at Week 16 and not receiving rescue therapy from Week 8 to Week 16. Proportion of subjects maintaining a vIGA score of 0 or 1 at Weeks 18, 20, 24 among those achieving a vIGA score 0 or 1 at Week 16 and not receiving rescue therapy from Week 8 to Week 16.

 Explore the durability of the treatment effect after cessation of treatment at Week 16. 	
 % change in EASI at Weeks 18, 20, and 24 compared to Week 16 among those not receiving rescue therapy from Week 8 to Week 16. % change in SCORAD at Weeks 18, 20, and 24 compared to Week 16 among those not receiving rescue therapy from Week 8 to Week 16.
Exploratory (Pharmacokinetic)	

 To evaluate the PK of RPT193 following administration of multiple oral doses of RPT193 administered orally QD for 16 weeks to subjects with moderate-to-severe AD. 	
 PK parameters at Week 2, 4, 8, 12, 16, and 18.
Exploratory (Pharmacodynamic)	

 To evaluate the effect of multiple oral doses of RPT193 administered orally QD for 16 weeks to subjects with moderate-to-severe AD on serum cytokines and chemokines. 	
 Change in serum CCL17 levels Change in serum CCL22 levels Change in serum cytokines.

 To evaluate the effect of multiple oral doses of RPT193 administered orally QD for 16 weeks to subjects with moderate-to-severe AD on peripheral blood T cell subsets. 	
 Change in T cell subset numbers or proportion.

 To evaluate the effect of multiple oral doses of RPT193 administered orally QD for 16 weeks to subjects with moderate-to-severe AD on skin gene expression signatures and microbiome. 	
 Changes in skin gene expression signatures relative to baseline at Week 4, 8, 12, 16, and follow-up using skin tape strips. Change in skin microbiome composition relative to baseline at Week 4, 8, 12, 16, and follow-up.

4.0 STUDY DESIGN

4.1 Overall Design

This is a randomized, double-blind, dose-ranging study in adults with moderate-to-severe AD who have had an inadequate response to topical therapies or in whom topical therapies are contraindicated with a treatment duration of 16 weeks (112 days).

This study will assess RPT193 as monotherapy for the treatment of AD.

After the treatment period, there is a follow-up period ending at Day 169.

[figure not shown]
4.2 Scientific Rationale for Study Design

The proposed design is considered appropriate for assessing the efficacy and safety of RPT193 in subjects with moderate-to-severe AD.

This Phase 2 study will be randomized to ensure random allocation of subjects to treatment arms to reduce bias. Because efficacy assessments of AD can have a high degree of subjectivity, the study will be double-blinded. The highest degree of subject and assessor blinding should be sought to achieve credible inference. It is also important to have a placebo control to account for confounding factors, such as potential Investigator bias, and to ensure that the statistical procedures can be appropriately applied. The inclusion of 3 dose strengths of RPT193 across an 8-fold dosing range is designed to identify a sub-efficacious as well as a minimally effective dose.

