4.3 Justification for Dose

RPT193-02 will investigate the efficacy and safety of RPT193 in subjects with moderate-to-severe AD. The study will assess 3 doses of RPT193 (50, 200, and 400 mg) taken orally QD for 16 weeks.

[REDACTED]

[REDACTED]

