9.2 Sample Size Determination

[REDACTED]

- | [REDACTED]
- | [REDACTED]
- | [REDACTED]
- | [REDACTED]

Based on the assumptions above and using a two-sample t-test, a sample size of 60 subjects per treatment group is needed to detect the treatment effect on the primary endpoint between RPT193 and placebo. Assuming a 10% drop out rate, a total sample size of approximately 265 subjects (approximately 67 per treatment group) will be needed.

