9.4.2.2 Multiplicity

For the primary efficacy endpoint, to preserve the Type I error at 0.05, a serial gatekeeping strategy will be employed to address the multiplicity of the pairwise comparison of each RPT193 dose vs. placebo. The order of the testing will be performed from the highest RPT193 dose to the lowest dose. Testing will stop if non-significance (2-sided p-value ≥ 0.05) is observed.

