## **G. Multiple Comparisons**

For the primary efficacy endpoint of percent change from baseline in EASI at Week 16, to preserve the Type I error at 0.05, a serial gatekeeping strategy will be employed to address the multiplicity of the pairwise comparison of each RPT193 dose group vs. placebo. The order of the testing will be performed from the RPT193 400mg, 200mg to 50mg. Dose comparisons for percent change from baseline in EASI at Week 16 will stop when non-significance (2- sided p-value  $\geq 0.05$ ) is observed.

Analyses of secondary and exploratory endpoints will be presented without adjustment for multiplicity.

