### C. Primary Efficacy Analysis

The primary endpoint is the percent change in EASI from baseline to Week 16. The primary analysis will be based on the FAS and will use control-based PMM-MI to handle missing data.

The primary efficacy endpoint will be analyzed with an ANCOVA model. The model will include treatment group (each RPT193 dose vs. placebo), the randomization stratification factors of baseline vIGA score (3,4), and prior dupilumab or tralokinumab use (yes or no), and baseline EASI score as a covariate.

For each imputed dataset the least square (LS) mean, and LS mean difference in the percent change from baseline between each RPT193 dose level and placebo along with the corresponding estimated standard error will be reported. These results will be combined in PROC MIANALYZE using Rubin's formula and the resulting p-value will be used for inference at the 0.05 level of significance. The LS mean and LS mean difference along with the 95% confidence interval (CI) and p-value will be reported.

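### The stated dose-finding aim has no pre-specified dose-response analysis or decision rule, and non-significance at about 60 per arm cannot identify a sub-efficacious dose

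*Protocol*

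**What the plan says.** Protocol 4.1 calls the trial dose-ranging, and Protocol 4.2 says the three dose strengths are "designed to identify a sub-efficacious as well as a minimally effective dose". The synopsis and SAP I.A add that the data will inform later studies, including pivotal ones. Protocol 4.3 gives the doses: "The study will assess 3 doses of RPT193 (50, 200, and 400 mg) taken orally QD for 16 weeks". The rest of that section is redacted.

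On inference, Protocol 9.4.2.2 says that "to preserve the Type I error at 0.05, a serial gatekeeping strategy will be employed" and that "Testing will stop if non-significance (2-sided p-value ≥ 0.05) is observed". SAP IV.G fixes the sequence: "The order of the testing will be performed from the RPT193 400mg, 200mg to 50mg". It leaves secondary and exploratory endpoints unadjusted and outside the stop rule.

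On estimation, SAP VI.C reports for each imputed dataset the "LS mean difference in the percent change from baseline between each RPT193 dose level and placebo", then a pooled difference, 95% CI and p-value. MMRM means by visit and group are a sensitivity analysis, and SAP VI.D models the key secondary endpoints by dose. The SAP Appendix II example code requests all pairwise LS mean differences (`pdiff=all` for ANCOVA, `pdiff` for MMRM), which includes active against active. The SAP text names only the placebo contrasts.

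PK and PD analyses are left to separate plans (SAP I.B).

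**The concern.** Finding a sub-efficacious and a minimally effective dose is a question about the shape of the dose-response relation. The plan answers a different one: which doses, taken in order from the top, differ significantly from placebo. With no definition of the two labels and no rule for assigning them, p≥0.05 or not being reached in the chain is the only formal criterion a reader of the results will have. If the arms are too small for a partly active dose to reach significance reliably, that criterion confuses lack of evidence with lack of effect. The choice of doses for later trials is at stake. Each placebo contrast also estimates a dose effect from one active arm and placebo, although all four arms inform the curve.

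**Working it through.** **Inputs.** 60 evaluable per group, two-sample t-test, 10% dropout (Protocol 9.2, SAP III.C); two-sided 0.05; order 400, 200, 50 mg; allocation 1:1:1:1. Effect, SD and power are redacted, so I assume design power of 80–90%, with 95% as an extreme.

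**The plan's own figure.** The 60 per group cannot be reproduced without the redacted inputs. The dropout step can: 60/0.9 = 66.7, so 67 per group, and 4 × 67 = 268 (SAP exactly; the protocol says approximately 265).

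**Implied standardised effect.** d = (1.96 + z_power) × √(2/60).
- 80%: 2.80 × 0.1826 = 0.51
- 90%: 3.24 × 0.1826 = 0.59

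**Pairwise power at half the effect, n = 60.** Φ((1.96 + z_power)/2 − 1.96).
- 80%: Φ(1.40 − 1.96) = 0.29
- 90%: Φ(1.62 − 1.96) = 0.37

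**Through the chain.** Simulation with a shared placebo arm, 400,000 runs, 400 mg at full effect and 50 mg at half. The range covers 200 mg at full effect or at 75% of it.

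| Assumed design power | 50 mg declared, n=60 | 50 mg missed, n=60 | 50 mg missed, n=67 |
|---|---|---|---|
| 80% | 0.22–0.26 | 74–78% | 71–75% |
| 90% | 0.31–0.35 | 65–69% | 61–65% |
| 95% | 0.39–0.43 | 57–61% | 53–56% |

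**Stop rule or pairwise power?** At 80%, pairwise 0.288 against chain 0.259 or 0.220: a loss of 2.9 to 6.8 points. At 90%, 0.367 against 0.352 or 0.312: 1.5 to 5.5 points. Most misses come from the single comparison.

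**Sensitivity to the redaction.** Half-effect pairwise power reaches 50% when z_power = 2 × 1.96/√(n/60) − 1.96. That is 1.96 at n=60 (design power 97.5%) and 1.75 at n=67 (96%). Below those values, a miss is the more likely outcome.

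**What the per-dose CI can show.** Half-width divided by full effect is 1.96/(1.96 + z_power): 0.70 at 80% and 0.60 at 90%. An interval centred on half the effect, 0.5 ± 0.6 or 0.5 ± 0.7, contains both zero and the full effect.

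**What a contrast over all four arms gives.** At n=60, with effects of 0.5/0.75/1 of the full effect at 50/200/400 mg and 80% design power, a linear trend has power of about 0.76, an Emax-type contrast (ED50 of 50 mg assumed) 0.83, and the best possible contrast about 0.84. The top-dose pair has 0.80. At 90% design power the first two are 0.87 and 0.92. The gain in testing is modest and depends on shape.

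**What a fitted curve gives.** At 67 per arm, the pairwise estimate of the lowest-dose effect has RMSE √(2/67) = 0.173 SD units. An Emax fit gives 0.102 to 0.155 across five smooth and plateau shapes, a reduction of 10–41%. But with 50 mg inactive and 200 and 400 mg at full effect, it overstates the 50 mg effect by about 36% of the top-dose effect, and RMSE rises to 0.203.

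**The case against.** A fixed sequence of pairwise tests controls Type I error and is a legitimate Phase 2 choice. The chain is not the whole of the dose information: the SAP gives per-dose differences with 95% CIs, MMRM means, and key secondary comparisons free of the stop rule. Its example code already asks for active-versus-active differences. Exposure-response work may sit in the separate PK and PD plans or behind the redacted dose justification. All of this stands.

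A reader might infer that the plan will label a non-significant dose ineffective. Neither document says so; the gap is that nothing says what would support either label. A reader might also infer that no two active doses are compared, but the example code requests those differences; the text simply does not commit to reporting them. Nor is the stop rule the main cause of the low success rate.

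The objection also limits the remedy. A trend test does not show that the lowest dose works, a linear trend can have less power than the top-dose pair, and Emax alone misleads in exactly the case the aim names, an inactive low dose. These points shape the fix but do not close the gap. The placebo-based efficacy estimates are still pairwise, and their intervals are too wide to place a half-effect dose.

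**Conclusion.** The concern holds in this form: the stated dose-finding aim has no pre-specified dose-response or trend analysis in these documents and no rule connecting results to it. Under 80–90% assumed design power at 60 per arm, a 50 mg dose with half the design effect would miss significance in roughly 65–78% of trials (61–75% if 67 per arm are analysed). The actual effect and power are redacted, but misses outnumber successes for any design power below about 96–97.5%. Covariate adjustment could raise power somewhat and placebo-based imputation would lower it; neither can be quantified from the documents. The confirmatory test remains valid. What cannot be supported is reading p≥0.05, or a dose left untested in the chain, as evidence that the dose is sub-efficacious.

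**What to change.** Keep the 400, 200, 50 mg chain as the only confirmatory test. Make three additions to SAP VI.C. SAP I.B allows changes until treatment unblinding, so they should be in place before the unblinded Week 16 analysis described in SAP IV.F.

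1. One supportive dose-response analysis: take the four adjusted Week 16 means from the 100 imputed datasets, pool by Rubin's rules, and apply MCP-Mod with a candidate set that includes linear, Emax and a sigmoid or step-like shape, not Emax alone. Report the trend test and the fitted curve. A sigmoid Emax with all four parameters free would be saturated by four dose levels, so fix its steepness in advance.
2. A sentence in the text committing to report the active-versus-active LS mean differences with 95% CIs that the example code already requests.
3. A statement that any sub-efficacious or minimally effective description rests on the per-dose and between-dose CIs read alongside the curve, not on p≥0.05 or on a dose being untested.

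The cost is SAP wording and a few days of programming, with no new data and no change to alpha. The downside is that a curve through four dose levels depends on the model, and an Emax-only fit can make an inactive low dose look partly active. The analysis must therefore stay supportive.

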4.3 Justification for Dose

RPT193-02 will investigate the efficacy and safety of RPT193 in subjects with moderate-to-severe AD. The study will assess 3 doses of RPT193 (50, 200, and 400 mg) taken orally QD for 16 weeks.

[REDACTED]

[REDACTED]

4.4 End of Study Definition

A subject is considered to have completed the study if he/she has completed all phases of the study including a 35-day maximum screening period (Day -35 to Day -1), a 16-week double-blind treatment period (Day 1 to Day 113/Week 16) and an 8-week follow-up period (Day 113/Week 16 to Day 169/Week 24).

The end of the study is defined as the completion of the last visit or procedure shown in the SoA for the last enrolled subject in the trial for all sites.

5.0 STUDY POPULATION

Prospective approval of protocol deviations to recruitment and enrollment criteria, also known as protocol waivers or exemptions, is not permitted.

5.1 Inclusion Criteria

Subjects are eligible to be included in the study only if all of the following criteria apply:

1. Male or female subject aged 18 to 75 years, inclusive, at the time of consent.
2. Subject has clinically confirmed diagnosis of active AD, according to the revised Hanifin and Rajka criteria. [Eichenfield 2014]
3. Subject has at least a 12-month history of AD and had no significant flares in AD for at least 4 weeks before Screening, as determined by the Investigator through subject interview at the Screening visit or information obtained from medical chart or subject's physician.
4. Subject has a documented history of inadequate response to a ≥ 1 month treatment with topical medications, such as class I-V topical corticosteroids, topical PDE4 inhibitor (e.g., crisaborole), and/or calcineurin inhibitors in the 6 months prior to the Screening visit or subjects for whom topical treatments are otherwise medically inadvisable.
5. Subject has AD covering $\geq 10\%$ of the BSA.
6. Subject has an EASI score ≥ 16 at Screening and at Baseline.
 - Subjects may be screened with an EASI score ≥ 12 if the subject is administering class I-V topical corticosteroids, topical PDE4 inhibitor (e.g., crisaborole), and/or topical calcineurin inhibitors or is using systemic immunosuppressants (e.g., methotrexate, cyclosporine A, mycophenolic acid, azathioprine, and/or systemic corticosteroids); eligibility for the study requires follow-up EASI score ≥ 16 at Baseline (after the relevant washout period for the index medication has been satisfied).
7. Subject has a Validated Investigator Global Assessment (vIGA) score ≥ 3 .
8. Subject has been using one or more emollient(s) (except urea-containing emollients or medicated emollients that are regulated as a medical device) at least twice daily for 1 week prior to Baseline (except on visit day before the visit) and agrees to continue using the same emollient(s) daily at the same frequency (at least twice daily) throughout the study.

Notes: On the day of scheduled visit, subjects cannot apply emollient before their scheduled visit, and every effort should be made to use the same emollient throughout the study for the same body region. However, the chosen emollient may differ depending on the body region (e.g., body vs face emollient may be different).
9. Female subject of childbearing potential has had a negative serum pregnancy test at Screening and negative urine pregnancy test at Baseline.
10. For female subject of childbearing potential involved in any sexual intercourse that could lead to pregnancy: the subject must agree to use a highly effective contraceptive method from at least 4 weeks prior to Day 1 until at least 30 days after the last study drug administration. Highly effective contraceptive methods include hormonal contraceptives (e.g., combined oral

contraceptive, patch, vaginal ring, injectable, or implant), intrauterine devices or intrauterine systems, vasectomized partner(s), tubal ligation or double barrier methods of contraception (e.g., male condom with cervical cap, male condom with diaphragm, and male condom with contraceptive sponge) in conjunction with spermicide.

Notes:

- For countries where double barrier methods are not accepted as highly effective contraception, then this option must not be considered.
 - A female subject of nonchildbearing potential is defined as follows:
 - Female subject who has had surgical sterilization (hysterectomy, bilateral oophorectomy, or bilateral salpingectomy)
 - Female subject who has had a cessation of menses for at least 12 months prior to the Screening visit without an alternative medical cause, and a follicle-stimulating hormone (FSH) test confirming nonchildbearing potential (refer to laboratory reference ranges for confirmatory levels).
 - Subjects must have been on a stable regimen of hormonal contraceptives for at least 4 weeks prior to Baseline.
 - The above list of contraceptive methods does not apply to subjects who are abstinent for at least 4 weeks before Baseline (Day 1) and will continue to be abstinent from penile-vaginal intercourse throughout the study. The reliability of sexual abstinence needs to be evaluated in relation to the duration of the clinical trial and the preferred and usual lifestyle of the participant.
11. Female subject agrees not to have egg retrieval during the study and for 30 days after the last study drug administration.
 12. For male subject involved in any sexual intercourse that could lead to pregnancy, subject must agree to use one of the highly effective contraceptive methods listed in Inclusion Criterion #10, from Baseline (Day 1) until at least 90 days after the last study drug administration. If the female partner of a male subject uses any of the hormonal contraceptive methods listed above, this contraceptive method should be used by the female partner from at least 4 weeks before Baseline (Day 1) until at least 90 days after the last study drug administration.
 13. Male agrees not to donate sperm during the study and for 90 days after the last study drug administration.
 14. Subject has negative COVID-19 results at Screening.
 15. Subject is willing to comply with discontinuation of prohibited treatments for AD as described in [Table 3](#) for the duration of the study, as directed by the Investigator.
 16. Subject is willing to participate and is capable of giving informed consent.
Note: Consent must be obtained prior to any study-related procedures.
 17. Subject must be able and willing to comply with all study procedures and must be available for the duration of the study.

